5.3. Lifestyle Considerations

No restrictions to lifestyle considerations are required for this study. However, as indicated in [Section 5.1](#) (inclusion criterion 6), participants must agree to refrain from making any major changes in diet, weight, exercise, or other major lifestyle patterns after signing the ICF and through the EoS Visit.

5.3.1. Meals and Dietary Restrictions

Refrain from consumption of Seville oranges, grapefruit or grapefruit juice for a minimum of 7 days prior to starting study drug until after the final dose.

The study drug should be taken by participants approximately 30 minutes before a meal 3 times a day and 30 minutes before bedtime, with a minimum interval of 4 hours between doses.

Day 1 and Week 2 Visits:

For the Day 1 and Week 2 PK assessments, participants who are not in the Intensive PK Subset should arrive at the clinic in the morning after fasting (water is allowed) for at least 4 hours, and either prior to taking any study drug or within 4 to 6 hours after the first dose of study drug of the day. (See also [Section 8.7.1.](#))

For the Day 1 and Week 2 PK assessments in the Intensive PK Subset, participants should arrive at the clinic in the morning after fasting (water is allowed) for at least 8 hours and prior to the first dose of study drug of the day. (See also [Section 8.7.1.](#))

At the Day 1 and Week 2 visits, study drug should be administered in the clinic approximately 30 minutes before eating. The first dose should be administered with 240 mL of water. No additional water is permitted until 30 minutes after dosing, after which time, water is allowed ad libitum.

5.3.2. Caffeine, Alcohol, and Tobacco

The intake of alcohol, caffeine and tobacco should not be increased during the study.

5.3.3. Activity

No study-specific activity restrictions apply, except to refrain from making any major changes in diet, weight, exercise, or other major lifestyle patterns after signing the ICF and through the EoS Visit.

5.4. Screen Failures

Screen failures are defined as participants who consent to participate in the clinical study but are not subsequently entered in the study. A minimal set of screen failure information is required to ensure transparent reporting of screen failure participants to meet the Consolidated Standards of Reporting Trials publishing requirements and to respond to queries from regulatory authorities. Minimal information includes demography, reason for screen failure, and any serious adverse event (SAE).

Participants who do not initially meet study Screening criteria (ie, are screen failures) may be re-screened (no more than 1 additional Screening) after consultation with and approval by the sponsor Medical Monitor or designee.

5.5. Pretreatment Period Failures

Pretreatment failures are defined as participants who do not meet the prespecified criteria for eligibility regarding the Pretreatment Period assessments (see [Section 5.1](#), inclusion criterion 4).

Participants who are pretreatment failures may be re-screened upon approval from the sponsor and/or Medical Monitor or designee.

6. Study Drug

Study drug is defined as any investigational intervention(s), marketed product(s), placebo, or medical device(s) intended to be administered to a study participant according to the study protocol.

6.1. Study Drug(s) Administered

The study drugs planned for use are described in [Table 1](#) below:

Table 1: Study Drugs

Arm Name	NG101 5 mg Arm	NG101 10 mg Arm	NG101 20 mg Arm	Placebo Arm
Intervention Name	Metopimazine mesylate	Metopimazine mesylate	Metopimazine mesylate	Placebo
Type	Drug	Drug	Drug	Placebo
Dose Formulation	Capsule	Capsule	Capsule	Capsule
Dosage Level(s)	NG101 5 mg, QID	NG101 10 mg, QID	NG101 20 mg, QID	Placebo, QID
Route of Administration	Oral	Oral	Oral	Oral
Use	Experimental	Experimental	Experimental	Placebo comparator
IMP and NIMP	IMP	IMP	IMP	NIMP
Sourcing	Provided by the sponsor	Provided by the sponsor	Provided by the sponsor	Provided by the sponsor
Packaging and Labeling	NG101 5 mg capsules will be provided in a blister pack labeled as required per country requirement	NG101 10 mg capsules will be provided in a blister pack labeled as required per country requirement	NG101 20 mg capsules will be provided in a blister pack labeled as required per country requirement	Placebo capsules will be provided in a blister pack labeled as required per country requirement

Study drug will be dispensed at each visit during the Treatment Period. Each participant will also be dispensed an extra blister pack in case dispensed study drug becomes depleted. Participants will be required to return for clinic visits with all dispensed medication (ie, study drug and rescue medication) to ensure use is recorded properly. Note that during the following visits, study drug will be administered in the clinic:

- **Day 1:** first dose in the clinic, and second dose of the day in the clinic for those participants in the Intense PK subset
- **Week 1:** a dose in the clinic (ie, not necessarily the first dose of the day)
- **Week 2:** first dose of the day in the clinic
- **Week 12:** a dose in the clinic (ie, not necessarily the first dose of the day)

All study drug capsules will be identical in appearance in order to maintain the blind.

Participants in the 20 mg treatment arm will be titrated up to the target dose in a blinded fashion. Specifically, the 20 mg arm initiation blister pack will contain a 4-day supply of 5 mg QID, and a 3-day supply of 10 mg QID, after which the blister packs will contain a 7-day supply of 20 mg QID. (Note: For participants in the placebo, 5 mg, or 10 mg arms, the blister pack will contain only the assigned treatment doses.)

If a dose is missed, (eg, not taken by at least 1 hour after a meal), then participants should skip the missed dose and resume dosing with the next planned dose (30 minutes before the next meal or before bedtime).

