1.2. Schema

Primary endpoint: Change from baseline in the nausea severity score in the Diabetic and Idiopathic Gastroparesis Symptoms daily diary (DIGS-DD)

★ Clinic visit

* The 20 mg arm will initiate dosing with 5 mg QID for 4 days, followed by 10 mg QID for 3 days, and then (starting on Day 8) 20 mg QID

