1.3. Schedule of Activities (SoA)

Procedure	Screening Visit	Pre-treatment Visit	Treatment Period Visits						E/D Visit	EoS / Follow-up Visit	Notes	
	(up to 28 days before Day -14)	Day	Day	Week								
		-17 to -14	1	(± 2d)	2	(± 2d)	4	(± 2d)	8	(± 3d)	12	(± 3d)
Informed consent	X											
Inclusion and exclusion criteria	X		X									Recheck clinical status / check compliance before randomization on Day 1
Demography	X											
Medical history	X											Including prior treatments for gastroparesis (dose, regimen, duration), substance use and, for females, menstrual history
Gastric emptying test	X											FDA-approved breath test completed and assessed for eligibility in participants who have not completed the breath test or scintigraphy test within 12 months prior to Screening, or during the Screening Period. Must be a minimum of 7 days between the gastric emptying study and the start of the Pretreatment Period.

Procedure	Screening Visit	Pre-treatment Visit	Treatment Period Visits						E/D Visit	EoS / Follow-up Visit (14 ± 3 days after last dose)	Notes	
	(up to 28 days before Day -14)	Day	Day	Week								
		-17 to -14	1	(± 2d)	2	(± 2d)	4	(± 2d)	8	(± 3d)	12	(± 3d)
Physical examination	X		X				X	X	X	X	X	A physical exam including neurologic, cardiovascular, pulmonary, abdominal and breast exams will be performed at Screening, Day 1, and Weeks 4, 8, and 12 (or E/D) as well as at the Follow-up Visit. Height will be measured on Day 1. For females, menstrual cycle will be recorded during the study.
Weight	X	X	X	X	X	X	X	X	X	X	X	
Vital signs	X	X	X	X	X	X	X	X	X	X	X	Vital signs include oral temperature, pulse rate, respiratory rate, and blood pressure. Orthostatic vital signs will also be checked at Screening, and at the Day 1, Week 1, and Week 2 visits. See Section 8.4.2 .

Procedure	Screening Visit	Pre-treatment Visit	Treatment Period Visits						E/D Visit	EoS / Follow-up Visit (14 ± 3 days after last dose)	Notes	
	(up to 28 days before Day -14)	Day	Day	Week								
		-17 to -14	1	(± 2d)	2	(± 2d)	4	(± 2d)	8	(± 3d)	12	(± 3d)
12-lead ECG	X		X		X			X	X	X		On Day 1 and Week 2, ECGs will be performed in triplicate at the time of PK sampling (ie, predose and at 1 [near anticipated T_{max}], 2, and 3 hours postdose). For the Intensive PK subset, in addition to the ECG assessments described above, triplicate ECGs should be taken at hour 6 (on Day 1 and Week 2) as well as 1 and 2 hours after the second dose at the Day 1 visit. See Section 8.4.3 .

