Two participants in the MAD 15 mg Q6H group experienced OH (on Day 1 at Hour 1 after the first dose) and 1 participant in the MAD 30 mg Q6H group experienced OH (on Day 1 at Hour 1 after the first dose). No other episodes of OH occurred with subsequent dosing in these participants, and no other participants in these dose groups experienced OH. On the other hand, most participants in the MAD 45 mg Q6H group experienced OH, and more than half experienced episodes on multiple days during the dosing period. A similar trend was noted for orthostatic tachycardia.

Based on these results, the risk of OH appeared to be dose dependent, with the 45 mg and 60 mg doses associated with a higher risk for OH than the 15 mg and 30 mg doses. These data also suggest that with repeat dosing, participants adapt to the alpha-adrenergic inhibition, which is consistent with the literature on alpha-1 receptor antagonists approved for use in hypertension and benign prostatic hyperplasia ([Achari et al. 1998](#)).

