2.2.2. Previous Human Experience

Metopimazine (Vogalene[®]) has been used extensively as an antiemetic for over 40 years in France. In a dose-ranging open-label safety and tolerability study involving 38 patients undergoing chemotherapy, metopimazine was administered orally every 4 hours at increasing doses ([Herrstedt et al. 1997a](#)). A total of 36 patients completing 46 cycles of chemotherapy received 20, 30, 40, 50 and 60 mg oral metopimazine every 4 hours over a 44-hour period. The metopimazine dose-limiting toxicity was moderate to severe dizziness caused by OH, as seen in 0, 0, 17%, 42% and 50% of the patients at the respective dose levels. No information was provided on the timing of the occurrence of dizziness during the 44-hour period. Few other side effects were reported, and most were mild. A single possible extrapyramidal AE was observed in a patient in the 60 mg x 11 dose group. Metopimazine was demonstrated to be safe at a dosage of 30 mg, 6 times (180 mg) daily.

Further, in a randomized, double-blind comparison of ondansetron vs ondansetron plus metopimazine as antiemetic prophylaxis during platinum-based chemotherapy in patients with cancer, metopimazine was administered at 35 mg/m² IV followed by 30 mg, 4 times a

day (120 mg daily), for 4 days. A total of 94 patients completed the crossover study. Results suggested that metopimazine plus ondansetron was significantly superior to ondansetron alone on all efficacy parameters assessed. Reported adverse reactions were mild and without significant differences between the 2 treatments. However, an asymptomatic decrease in standing BP was observed when patients received the combination antiemetic therapy (Herrstedt et al. 1997a).

In a randomized, double-blind trial assessing the efficacy and safety of sublingual metopimazine compared to ondansetron in chemotherapy-induced delayed emesis, patients received either 45 mg/day of metopimazine (15 mg every 8 hours) or 16 mg/day of ondansetron (8 mg every 12 hours). Metopimazine was comparable in efficacy to ondansetron. Furthermore, the incidence of gastrointestinal (GI) disorders was significantly lower in the metopimazine group, particularly abdominal pain and constipation (Herrstedt et al. 1997b; Bethune-Volters et al. 2006).

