2.5.1. Risk Assessment

Potential Risk of Clinical Significance	Summary of Data / Rationale for Risk	Mitigation Strategy
Study Drug		
Orthostatic hypotension (OH)	
OH has been observed in the phase 1 studies with metopimazine free base (Vogalene) and NG101. This is likely due to partial alpha-1 receptor inhibition.
	
Exclusion criterion: Participants with severe postural symptoms and/or absolute systolic BP < 90 mm Hg upon standing.
 
Monitoring: During the study, participants will be observed in the clinic on Day 1 for 3 hours after taking the first dose of NG101 (approximately 1 to 2 hours after the time of maximum concentration [T_{max}]). At the Week 1 and Week 2 visits, participants will be observed for 2 and 3 hours after dosing, respectively. Participants will have hourly orthostatic BP and AE assessments while in the clinic for these visits.
 
Participants who have systolic BP that decreases at least 20 mm Hg upon standing, and who have concomitant postural AEs during study visits will be further assessed in the clinic and/or after returning home. Postural AEs can include feelings of lightheadedness, general weakness, warmth, diaphoresis, nausea, palpitations or blurry vision (Whitledge et al. 2019).
 
If, in the investigator's judgement, a participant's postural symptoms constitute a safety risk of potential harm upon release from the clinic, that participant will remain in the clinic under observation (beyond the scheduled observation on Day 1 and Weeks 1 and 2) with continued orthostatic BP and AE assessments. If the participant has persistent moderately symptomatic OH through the 6-hour dosing interval, or the investigator has significant concern that BP decreases and postural symptoms will recur upon subsequent dosing, the participant should receive the next dose under observation in the clinic.
 
If, in the investigator's medical judgement, the participant continues to be at significant risk of harm with continued dosing upon release from clinic, that participant will be stopped and withdrawn from the study. Otherwise, once the participant is asymptomatic for OH on 2 successive measurements, the participant may be released from the clinic, and will be contacted by phone after returning home that day, and on subsequent days as necessary, to monitor for

Potential Risk of Clinical Significance	Summary of Data / Rationale for Risk	Mitigation Strategy

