		
continued AEs. Participants with recurrent postural AEs on subsequent days will return to the study site for further evaluation.
 
Individual stopping criteria:
 
Participants with OH (defined by a decrease in systolic BP of at least 20 mm Hg) and associated severe postural symptoms will be stopped and withdrawn from the study.
 
These severe symptoms include presyncope, syncope, and other severe AEs that are considered of substantial clinical relevance by the investigator. Presyncope is defined as “feeling like one was going to pass out but without actual loss of consciousness” (Whitledge et al. 2019). Syncope is “the sudden loss of consciousness, associated with inability to maintain postural tone, with immediate and spontaneous recovery without requiring electrical or chemical cardioversion” (da Silva 2014).
 
Participants meeting this discontinuation criterion while under observation during clinical visits must be monitored in the clinic until postural symptoms are no longer severe, and will be withdrawn from the study. Participants who develop severe postural symptoms at home will hold any further dosing and return to the study site as soon as possible for further evaluation.
 
Other mitigation:
 
Participants in the 20 mg treatment arm will be initiated with a dose titration, beginning with daily dosing with 5 mg 4 times daily (QID).
 
Repeated dosing is associated with counter regulation to alpha blockade and reduction in blood pressure effects.
 
Participants will be trained to recognize signs and symptoms of OH, and how to manage it should it occur.
 
For the first 24 hours of dosing, participants should avoid situations in which injury might occur (eg, driving) should there be orthostatic symptoms.

Neuroleptic malignant syndrome (NMS)	Observed within the class of D ₂ antagonists	As a Pg-P substrate, metopimazine is not expected to have significant penetration of the CNS. Nevertheless, clinical assessment for early detection of NMS will be included in the study.

Potential Risk of Clinical Significance	Summary of Data / Rationale for Risk	Mitigation Strategy
Hyperprolactinemia-related effects, including gynecomastia, galactorrhea, menstrual irregularities, impotence, and decreased libido	Dopamine blockade is associated with increases in serum prolactin levels.	Clinical assessment for prolactin-related AEs.

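### The Week 1 orthostatic check is not tied to the Day 8 step to 20 mg, so a participant's first 20 mg dose can have no scheduled reading until Week 2

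*Combined protocol and SAP*

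**What the plan says.** **Titration.** Section 1.2 has the 20 mg arm take 5 mg QID for 4 days, 10 mg QID for 3 days, "and then (starting on Day 8) 20 mg QID". Under Section 6.1 the initiation pack covers those 7 days and later packs hold 20 mg. An extra pack is also dispensed, but its strength is not stated. The 5 mg and 10 mg arms are not titrated.

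**Readings.** Section 1.3 states: "Orthostatic vital signs will also be checked at Screening, and at the Day 1, Week 1, and Week 2 visits". Section 8.4.2 sets Week 1 readings at predose and 1 hour, and Week 2 readings at predose and 1, 2 and 3 hours, with others as the clinical picture requires. Section 2.5.1 describes a longer Week 1 stay: "At the Week 1 and Week 2 visits, participants will be observed for 2 and 3 hours after dosing, respectively", with hourly orthostatic checks.

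**Visit timing.** The Section 1.3 column headings are broken in the text available, but five windows line up with Weeks 1, 2, 4, 8 and 12, which gives Week 1 a window of ±2 days. Its nominal study day cannot be read. Section 6.1 makes the Week 1 clinic dose "a dose in the clinic (ie, not necessarily the first dose of the day"; at Week 2 it is the day's first dose.

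**Caution.** Section 2.5.1 states: "For the first 24 hours of dosing, participants should avoid situations in which injury might occur (eg, driving". The text does not repeat this advice at a dose step.

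**The concern.** In the 5 mg and 10 mg arms, the first dose at target strength is the Day 1 clinic dose, which has 3 hours of observation, hourly orthostatic checks and the 24-hour caution. In the 20 mg arm, the only one judged to need titration, all of that protection falls on a 5 mg dose. If the Week 1 visit comes before Day 8, the participant doubles the dose at home with no scheduled reading and no current advice to avoid driving.

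What is at stake is mainly participant safety at one step. Section 4.3 reports that orthostatic hypotension (OH) at 15 and 30 mg appeared on Day 1 at Hour 1. That suggests the first exposure to a dose is the one to watch. Those participants were not titrated, so carrying the pattern over to a step-up is an inference.

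**Working it through.** **Inputs.** Titration days: Sections 1.2 and 6.1. QID dosing: Section 6.1. Window of ±2 days for Weeks 1 and 2: Section 1.3. Arm size: 280/4 = 70 (Section 9.1, 1:1:1:1 allocation). Assumptions: Week 1 is nominally Day 7 or Day 8, Week 2 is nominally Day 14 or Day 15, and every dose is taken.

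**1. Reproduce the stated step day.** 4 + 3 = 7 days, so 20 mg starts on Day 8, as the schema says. Doses before the step: 4 × 4 + 3 × 4 = 28, so the first 20 mg dose is dose 29.

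**2. Gap after the caution.** The caution ends 24 hours after the first dose, on Day 2. 8 − 2 = 6 days before the step.

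**3. What a Week 1 visit reads in the 20 mg arm.**

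| Visit day | In window if nominally Day 7 | In window if nominally Day 8 | Dose read | Can it read the first 20 mg dose? |
|---|---|---|---|---|
| 5 | yes | no | 10 mg | no |
| 6 | yes | yes | 10 mg | no |
| 7 | yes | yes | 10 mg | no |
| 8 | yes | yes | 20 mg | only if the clinic dose is the first of the day |
| 9 | yes | yes | 20 mg | not if 20 mg was already at home |
| 10 | no | yes | 20 mg | not if 20 mg was already at home |

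So 3 of 5 allowed days (nominal Day 7) or 2 of 5 (nominal Day 8) fall on 10 mg. These are counts of days, not estimates of attendance.

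**4. When the next scheduled reading comes after an early visit.** 20 mg doses taken before the first dose of visit day d number 4 × (d − 8).

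- Week 2 at Day 14 ± 2: Day 12 gives 4 × 4 = 16; Day 14 gives 4 × 6 = 24; Day 16 gives 4 × 8 = 32.
- Week 2 at Day 15 ± 2: Day 13 gives 4 × 5 = 20; Day 15 gives 4 × 7 = 28; Day 17 gives 4 × 9 = 36.

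Section 5.3.1 also lets participants outside the intensive PK subset arrive after their first dose of the day, which would add one dose to each count.

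**5. Under the proposed visit rule.** The same formula, with the day's first dose in clinic and 20 mg at home, gives 0 for Day 8, 4 for Day 9 and 8 for Day 10.

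**The case against.** The case against has real weight.

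- **The text is incomplete.** The schema drawing is missing and the schedule headings are broken, so the original may show how visits line up with the titration. This stands as a caution. Even so, the written rules on the Week 1 dose and window contain no such tie, and a visit before Day 8 reads 10 mg on either nominal day.
- **The risk is low and already managed.** Phase 1 found "the 45 mg and 60 mg doses associated with a higher risk for OH than the 15 mg and 30 mg doses". In the earlier oncology study, dosed at 20, 30, 40, 50 and 60 mg, "The metopimazine dose-limiting toxicity was moderate to severe dizziness caused by OH, as seen in 0, 0, 17%, 42% and 50% of the patients", so none at 20 or 30 mg. Section 2.5.1 adds that "Repeated dosing is associated with counter regulation to alpha blockade and reduction in blood pressure effects". OH training, readings when clinically needed, return-to-site and stopping rules, the DSMB trigger and the Week 2 readings all remain. This stands, and it is why the point is small. None of these measures provides a scheduled reading of the first 20 mg dose.
- **The packs provide a partial link.** The initiation pack lasts exactly 7 days and drug is dispensed at each treatment visit, so 20 mg may not be at home before Week 1. This limits what can be said about visits on Day 9 or 10. It does not affect visits before Day 8.
- **The visit change needs supply.** Barring early visits without missed doses on slippage requires 20 mg at home. This stands and is made a condition of the fix.

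A reader might also infer that the titration's second aim, studying adaptation to alpha-1 blockade, is defeated because Week 1 mixes 10 mg and 20 mg readings. The documents do not support that. Adaptation is a repeat-dose effect that Week 2 still captures. Section 6.4 records the time of each clinic dose, and Section 9.3 leaves analysis detail to the SAP.

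**Conclusion.** The point holds as a low-cost safety improvement. As written, a 20 mg participant whose Week 1 visit falls before Day 8 has no scheduled orthostatic reading on 20 mg until Week 2, after about 16 to 32 doses (Day 14 ± 2) or 20 to 36 (Day 15 ± 2), with the injury caution about 6 days expired. The counts rest on assumed nominal days and full adherence. Section 6.1 has missed doses skipped, so actual counts may be lower.

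Two stronger readings go beyond the documents. A reader might infer that the whole arm steps up unobserved. The share could be anywhere from none to all of about 70, and a Day 8 visit with the first dose in clinic reads it fully. A reader might also infer a serious hazard at 20 mg. The dose-response evidence and existing safeguards point to a probably modest absolute risk, and the documents give no event rate for a titrated step.

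**What to change.** Apply the same rule in all four arms, so that nothing reveals the titrated one.

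1. Repeat the 24-hour caution about driving and injury at the change from the initiation pack to the next pack, on Day 8.
2. Set the Week 1 visit at Day 8, +2 days and not earlier, with the day's first dose taken in clinic and orthostatic readings at predose, 1 hour and 2 hours. This also brings Section 8.4.2 into line with the 2-hour observation in Section 2.5.1.

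**Cost.** Item 1 is a line of participant instruction. Item 2 reduces scheduling flexibility at one visit and carries a supply condition: the extra pack given on Day 1 must be of the post-initiation strength and labelled for use from Day 8 only, so that a Day 9 or 10 visitor does not miss doses. That visitor's first 20 mg dose may still go unread, so the change narrows the gap without closing it, and it gains nothing for Day 9 or 10 visitors who would already have had 20 mg at home. If the supply condition cannot be met, adopt item 1 alone.

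The doses and titration do not change. Tabulating Week 1 results by the dose actually taken is optional.
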